#### 2. INTRODUCTION

ALXN1830 is a humanized, affinity-matured IgG4 kappa mAb that binds to the FcRn and blocks FcRn-mediated recycling of IgG and IgG immune complexes (ICs), thereby lowering total IgG (including pathogenic autoantibodies) and ICs in circulation. As FcRn is also involved in albumin recycling, ALXN1830 was designed to specifically block the IgG-binding site but not the albumin-binding site on FcRn. Studies in both nonhuman primates and humans have demonstrated that ALXN1830 treatment leads to decreases in endogenous IgG levels without affecting serum albumin levels (Mezo, 2008; Nixon, 2015).

Immunoglobulin G can indirectly cause disease activity through the formation of ICs, which induce the production of inflammatory cytokines or promote antigen presentation and the pathogenic activity of T cells, which also provide help to B cells resulting in the production of additional pathogenic IgG antibodies (Blumberg and Lencer, 2005). The FcRn contributes to such immunopathology by both maintaining the levels of pathogenic IgG antibodies and orchestrating the inflammatory activities of IgG-ICs (Baker, 2009; Pyzik, 2015; Roopenian and Akilesh 2007).

There has been increasing recognition that FcRn blockade is a novel, reversible, and potentially effective means to treat a large number of autoimmune diseases in humans. The potential efficacy of FcRn blockade was originally supported by preclinical studies in experimental autoimmune myasthenia gravis (MG) in rats, wherein such FcRn blockade can impede both passive MG induced by administration of an anti-acetylcholine receptor antibody, or in active MG in rats that were immunized against the acetylcholine receptor (Liu, 2007). More recently, clinical studies in patients with MG and other IgG-mediated autoimmune diseases have demonstrated improvement in disease endpoints following treatment with anti-FcRn therapeutics.

While current treatments for certain autoimmune disorders, including chronic steroids, immunosuppressants, intravenous immunoglobulin (IVIG), plasmapheresis, and anti-CD20 mAbs (such as rituximab), can be effective, they are associated with significant adverse effects, and delayed or non-durable responses particularly in an elderly population. There remains a clear unmet medical need for the treatment of IgG-mediated diseases. Administration of ALXN1830, leading to a significant decrease in total IgG, pathogenic IgG autoantibodies, and the circulating immune complexes (CICs) of which these IgG are constituents, should lead to a decrease in the clinical manifestations of diseases of this type. Moreover, the ability of ALXN1830 to reduce CICs and the innate and adaptive immune responses triggered by CICs may result in sustained disease modification.

The purpose of this Phase 1 study in healthy adult participants is to evaluate the safety, tolerability, PK, PD, and immunogenicity of single ascending and once weekly (qw) multiple ascending SC doses of ALXN1830.

Data from this study are anticipated to help design future studies in patients with IgG-mediated diseases.

## 2.1. Study Rationale

ALXN1830 has been studied in 4 completed clinical studies using the IV route of administration. It was initially tested in an IV SAD study in healthy participants, Study SYNT001-101. The highest IV dose tested in the SAD study, 30 mg/kg, was well tolerated. ALXN1830 was then studied in 2 Phase 1b/2a studies in autoimmune patients: Study SYNT001-102 in warm autoimmune hemolytic anemia (WAIHA) patients, and Study SYNT001-103 in pemphigus vulgaris (PV) patients. In both studies, the participants received 5 qw doses of 10 mg/kg, a dose and regimen which was well tolerated.

Subsequently, a MAD study in healthy participants, Study SYNT001-104, was initiated to investigate the safety, tolerability, PK, PD, and immunogenicity of ALXN1830 IV. The dose level of the first cohort in the MAD study was 20 mg/kg IV, with 3 doses given qw ( $3 \times qw$ ) followed by 3 doses given every 2 weeks ( $3 \times q2w$ ). A second cohort was initiated using a dose level of 30 mg/kg, but the study was paused after 4 participants in Cohort 2 each received only a single dose due to the observation of acute infusion related reactions (IRRs) in the 20 mg/kg cohort.

SYNT001-102 and SYNT001-103 were also paused at that time for a Good Manufacturing Practice (GMP) investigation of the study drug batches. Although there was no conclusive clinical or safety link between the findings of the GMP investigation and the IRRs, and the drug product lots used had met all of the approved release specifications, the investigation did identify potential impurities in the drug product that could have possibly confounded the safety profile. Alexion has implemented changes to the manufacturing process for future batches to enhance the control and detection of impurities.

Another Phase 1 study in healthy participants using the SC route of administration, Study ALXN1830-HV-105, was initiated at a single site in the United Kingdom to investigate the safety, tolerability, PK, PD, and immunogenicity of single and multiple SC doses of ALXN1830. A total of 12 participants received a single SC dose of 750 mg (n = 6) or 1,250 mg (n = 3) or placebo (PBO; n = 3) before the study was terminated due to the coronavirus disease 2019 (COVID-19) pandemic. The highest SC single dose tested in this study, 1250 mg, was well tolerated.

The purpose of this Phase 1 study in healthy adult participants is to evaluate the safety, tolerability, PK, PD, and immunogenicity of single ascending and multiple ascending doses of ALXN1830 administered SC and to compare safety, tolerability, PK, PD, and immunogenicity of ALXN1830 in Japanese participants with non-Japanese participants. Data from this study are anticipated to help design future studies in patients with IgG-mediated diseases.

Healthy participants are the appropriate population for this study because they will enable PK and PD assessments without the potential confounding effects due to other disease activities, comorbidities, or medications. This study has been designed to minimize risks to participants with strict inclusion/exclusion criteria, as well as a robust safety monitoring and risk mitigation plan.

## 2.2. Background

A detailed description of the chemistry, pharmacology, efficacy, safety, and toxicology data available for ALXN1830 is provided in the Investigator's Brochure (IB).

Nonclinical studies have assessed both the potential toxicity and primary PD effects associated with ALXN1830 antagonism of IgG binding to FcRn and IgG recycling mediated by FcRn. The administration of ALXN1830 to cynomolgus monkeys by qw IV infusion at doses from 5 to 100 mg/kg for 2 to 27 weeks was well tolerated, with the exception of immunogenicity related effects of this humanized mAb in monkeys, and produced dose-dependent, specific, and reversible reductions in circulating IgG levels. No effects on IgA, IgM, or albumin levels were observed.

ALXN1830 has been evaluated in 4 completed clinical studies: SYNT001-101 (healthy participants, single dose study), SYNT001-102 (WAIHA patients, 5 × 10 mg/kg qw), SYNT001-103 (PV patients, 5 × 10 mg/kg qw), and SYNT001-104 (healthy participants, 3 × 20 mg/kg qw, then 3 × 20 mg/kg q2w), and 1 clinical study ALXN1830-HV-105, in healthy participants, was paused² after completing the first cohort and part of the second cohort (single SC doses of 750 mg and 1,250 mg). In all the clinical studies, ALXN1830 was shown to increase the catabolism of IgG, as manifested by decreased total IgG in serum in a dose-dependent manner up to 64% decrease from baseline, with no effects on IgA, IgM, or albumin. ALXN1830 also decreased the level of circulating IgG IC. This predicts that ALXN1830 will also accelerate degradation of endogenous circulating IgG autoantibodies and IgG IC specifically involved in the pathogenesis of autoimmunity.

#### 2.3. Benefit/Risk Assessment

This is a healthy participant study, and there is no direct benefit to study participants. However, the PK/PD data together with safety profiles without being confounded by underlying disease or concomitant medications, may benefit future human studies in general. Detailed risk assessment is listed in Table 13, as well as in the IB. In addition, a discussion of theoretical risks associated with the reduction of IgG is provided in Section 10.7.1.

 A temporary halt was implemented to allow assessment of the extent of SARS-CoV2 exposure in the UK.

#### 2.3.1. Risk Assessment

Table 13: Risk Assessment for ALXN1830

Identified and Potential Risk of Clinical Significance	Summary of Data/Rationale for Risk	Mitigation Strategy
	Study Drug (s) ALXN1830	
Infusion-Related Reaction	A total of 6 IRRs in clinical studies have been observed. The safety data may have been confounded by Chemistry and Manufacturing Control findings.	See Section 10.4 for IRR management.
Immunogenicity	Treatment with any therapeutic protein may induce an immune response. Occasionally, this immune response is clinically meaningful. The consequences of an immune reaction to a therapeutic protein range from transient appearance of antibodies, without any clinical consequence, to severe, life-threatening conditions. Potential clinical consequences also may include severe hypersensitivity-type reactions, decrease in efficacy, and induction of autoimmunity.	See SoA (Section 1.3 and Section 10.4 for IRR (including ADA associated IRR) management.

Abbreviations: ADA = antidrug antibody; IRR = infusion-related reaction.

#### 2.3.2. Benefit Assessment

As this is a study in healthy participants, only societal benefit is expected. Initial testing in healthy participants is warranted, as studies in patients, especially those with rare autoimmune diseases, may take years to accrue and complete. Healthy participant studies however may be completed more rapidly and without the multiple confounding variables of the underlying disease and concomitant medications. Also, for studies in healthy participants, the study duration is limited to the protocol-defined dosing regimen. Therefore, the total exposure is considerably less than what is likely to be required for patients who may require chronic dosing. Most adverse events (AEs) reported in previous studies with ALXN1830 were nonserious and resolved with discontinuation of study drug. While the potential of serious AEs or unexpected AEs exists, this healthy participant study will provide meaningful scientific information which will continue to play an important role in future development of this drug.

#### 2.3.3. Overall Benefit: Risk Conclusion

ALXN1830 was well tolerated after single doses up to 30 mg/kg IV and 1250 mg SC (the highest single doses tested in SAD studies) in healthy adults. Also, ALXN1830 was well tolerated after multiple IV doses at 10 mg/kg × 5 doses in autoimmune patients. However, at multiple IV doses of 20 mg/kg in healthy participants, the development of potentially immune mediated IRRs that resulted in immediate and permanent discontinuation of study drug, together with 100% incidence rate of headache, suggested that close safety monitoring and implementation of risk mitigation measures are warranted for future studies in the clinical development program (Section 10.6). Of note, these IRRs were mild and moderate in severity and all resolved after cessation of the study drug, without treatment. Similarly, all AEs of headache were mild to moderate and were resolved.

As described in Section 2.1, potential impurities in the drug product could possibly have confounded the safety profile. Alexion has implemented changes to the manufacturing process for the current and future batches to enhance the control and detection of impurities.

The proposed safety measures in this study include documentation of pneumococcal and current seasonal flu vaccination; staggered dosing; stopping rules; close participant monitoring through 60 days after the last dose; close safety and PD monitoring with an unblinded medical monitor; avoidance of participants with a high risk of infections; antibiotics to manage infection as needed; rescue measures such as IVIG replacement in an extremely unlikely event of profoundly low IgG; as well as use of an SRC for safety monitoring and dose selections.

Considering the measures taken to minimize risk to participants in this study, the risks associated with ALXN1830 are justified by the anticipated benefits that may be afforded to patients with autoimmune disease.

# 3. OBJECTIVES AND ENDPOINTS

# **Objectives and Endpoints:**

Objectives	Endpoints		
Primary			
To assess the safety and tolerability of single and multiple doses of ALXN1830 SC	Safety assessed by the incidence and relatedness of TEAEs, SAEs, AESIs, physical examination, vital sign measurements, clinical laboratory, and ECG results		
Secondary			

 
To assess the PK of single and multiple doses of ALXN1830 SC
 
To explore the PD effects of single and multiple doses of ALXN1830 SC
 
To assess the immunogenicity of ALXN1830 SC
 
To compare safety and tolerability, PK, PD, and immunogenicity of ALXN1830 SC between Japanese and non-Japanese healthy participants
 
	
 
Serum ALXN1830 concentration profiles and single-and multiple-dose PK parameters
 
Change in serum IgG levels over time; FcRn saturation as measured by receptor occupancy
 
Incidence of antidrug antibodies and neutralizing antibodies to ALXN1830
 
Quantitative assessment of safety, PK parameters, PD parameters, and immunogenicity between Japanese and non-Japanese healthy participants
 
		

Abbreviations: AESI = adverse events of special interest; ECG = electrocardiogram; FcRn = neonatal crystallizable fragment receptor; IgG = immunoglobulin G; PD = pharmacodynamics; PK = pharmacokinetics; SAE = serious adverse event; SC = subcutaneous; TEAE = treatment-emergent adverse event.

#### 4. STUDY DESIGN

# 4.1. Overall Design

This is a Phase 1 study in up to a maximum of 48 healthy adult participants (36 on active treatment, 12 on PBO). The study will consist of 2 SAD (Cohorts 1 and 2) and 4 MAD cohorts (Cohorts 3 to 6). Cohort 6 will enroll Japanese participants. Eight participants will be randomly assigned in a 6:2 ratio in each of the 6 cohorts to receive either single or multiple SC doses of ALXN1830 (n = 6 per cohort) or single or multiple doses of PBO (n = 2 per cohort). The planned study duration is approximately 124 days for Cohorts 1 and 2: up to 60 days for screening and approximately 64 days for dosing and follow-up; 201 days for Cohort 3: up to 60 days for screening and approximately 141 days for dosing and follow-up; and 148 days for Cohorts 4 to 6: 60 days for screening and approximately 88 days for dosing and follow-up. Participants will be admitted to an inpatient facility during the dosing and follow-up period as shown in Section 1.3.

Initially, the first 4 participants randomized to each cohort will be dosed with 3 participants on active treatment and 1 participant on PBO. The dosing will be staggered, with an interval of at least 3 days for the SAD cohorts and at least 7 days for the MAD cohorts, before dosing the rest of the participants in the cohort. The shorter interval of staggered dosing for the SAD cohorts compared to the MAD cohorts is considered appropriate as the expected PK exposure of the ALXN1830 SC doses will be a fraction of that of the IV dose demonstrated to be safe and well tolerated in previous IV studies. The reduction of IgG after a single SC dose will be similar to the observed IgG reduction in previous IV studies; and in general, there will be low risk of immunogenicity and IRRs after a single dose. See Section 4.3 for details regarding expected PK exposures and IgG reduction. All participants will be observed during the drug administration and for 2 hours after dosing for safety and participants will be encouraged to report any discomfort immediately, especially within 24 hours post dosing. At no time will more than 4 participants per cohort be dosed on a given day.

An SRC, consisting of the Investigator, and Alexion Safety Physician, Medical Monitor, Study Statistician, and Clinical Pharmacologist, will evaluate the study data at prespecified time points for participant safety and make recommendations on dose escalation, dose modification, or termination of the study (see SRC charter for description of membership, schedule of meetings, data required for each safety review, and requirements for documenting meeting discussions and outcome). Relevant safety data from any other studies ongoing with ALXN1830 will be made available to the SRC. At Alexion's discretion, and after consultation with the SRC, additional participants may be enrolled as replacement participants only if a participant discontinues within 3 weeks of the last dose for reasons other than drug-related AEs.

The timing and dependencies of the dosing cohorts are described in Table 14 and Table 15.

Table 14: Planned Dose and Dose Regimens of ALXN1830 in Healthy Participants

Cohort No.	Regimen/Route of Administration	Study Drug (N)
1	Single dose SC	Placebo (n = 2) or
		$ALXN1830\ 1500\ mg\ (n=6)$
2	Single dose SC	Placebo $(n = 2)$ or
		ALXN1830 2250 mg (n = 6)
3	Multiple dose (12 doses qw) SC	Placebo $(n = 2)$ or
		ALXN1830750  mg  (n = 6)
4	Multiple dose (4 doses qw) SC	Placebo $(n = 2)$ or
		ALXN1830 1500  mg  (n = 6)
5	Multiple dose (4 doses qw) SC	Placebo $(n = 2)$ or
	-	ALXN1830 2250 mg (n = 6)
6 a	Multiple dose (4 doses qw) SC	Placebo (n = 2) or
	Japanese healthy participants	ALXN1830 HTD (n=6)

<sup>a Healthy, Japanese participants enrolled in Cohort 6 will be dosed according to the HTD established in the non-Japanese cohorts.

Abbreviations: qw = weekly; SC = subcutaneous; HTD = highest tolerated dose.

**Table 15:** Minimum Data Requirements for Dose Escalation

Decision- making Time Point:	Dosing Regimen	Person or Body Making the Decision:	Minimum Data to be Looked at (in Accordance With the CSP):	Method of Documentation of Decision and/or Communication to Alexion (if Applicable):
Continuation from any sub-cohort to the next sub- cohort, within any cohort	As per relevant cohort	ΡΙ	A minimum of 3 days (SAD) / 7 days (MAD) post-dose safety and tolerability data from the first sub-cohort.	The Investigator will document the decision in an email to Alexion. The email does not require Alexion's response, unless there is disagreement with the Investigator's decision.
Cohort 1	1500 mg, single dose SC	N/A	N/A	N/A
Cohort 2	2250 mg, single dose SC	SRC	Review all available safety data and IgA, IgG, and IgM data through Day 15 from Cohort 1, from a minimum of 6 participants.	The SRC will document the decision on the escalation/progression approval form.
Cohort 3	750 mg, 12 doses SC, once weekly	SRC	N/A This cohort may start in parallel to Cohort 1.	N/A
Cohort 4	1500 mg, 4 doses SC, once weekly	SRC	Review all available safety data and IgA, IgG, and IgM data through Day 22 from Cohort 3, from a minimum of 6 participants.	The SRC will document the decision on the escalation/progression approval form.
Cohort 5	2250 mg, 4 doses SC, once weekly	SRC	Review all available safety data and IgA, IgG, and IgM data through Day 22 from Cohort 4, from a minimum of 6 participants.	The SRC will document the decision on the escalation/progression approval form.
Cohort 6 a	HTD, 4 doses SC, once weekly	SRC	Review all available safety data and IgA, IgG, and IgM data through Day 22 from Cohort 5.	The SRC will document the decision on the escalation/progression approval form.

<sup>a Healthy, Japanese participants enrolled in Cohort 6 will be dosed according to the HTD established in the non-Japanese cohorts.

Abbreviations: CSP = Clinical Study Protocol; HTD = highest tolerated dose; Ig = immunoglobulin; MAD = multiple ascending dose; N/A = not applicable; PI = Principal Investigator; PK = pharmacokinetics; SAD = single ascending dose; SC = subcutaneous; SRC = Safety Review Committee.

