As shown in Table 16 the first MAD cohort will be administered 750 mg SC qw for 12 weeks (Cohort 3). On a mg/kg basis, the 750 mg SC qw dose represents at least a 7 to 35-fold safety margin when compared to the NOAEL exposures of the 5-week SC and 27-week IV monkey GLP studies. The first MAD cohort (750 mg, qw, Cohort 3) may start at the same time as the single-dose Cohort 1 (1500 mg) while the rest of the MAD cohorts will start after SRC review of the previous MAD cohorts. While all the MAD cohorts have a treatment duration of 4 weeks, Cohort 3 (750 mg SC qw for 12 weeks) is of an extended duration to enable the evaluation of immunogenicity and safety after long term administration of ALXN1830.

The SC multiple doses will be escalated 2-fold from 750 mg qw to 1500 mg qw (Cohort 4), and then 1.5-fold to 2250 mg qw (Cohort 5) after SRC review. At these dose levels, the expected maximum IgG reduction after 4 qw doses is expected to be around 69% and 72%, respectively, which is similar to that observed with 20 mg/kg IV in Study SYNT001-104 (after the 3 qw loading doses).

As shown in Table 15, Cohort 6 will assess the safety, tolerability, PK, PD, safety, and immunogenicity of ALXN1830 in Japanese participants at the highest tolerable dose established in the non-Japanese participants (ie, either up to 1500 mg or up to 2250 mg SC qw for 4 doses). The exact dose and time of dosing will be determined after SRC review of all safety data through Day 36 from Cohort 5 as well as from all prior cohorts. Japanese participants are expected to have a lower mean body weight than non-Japanese participants. This and other differences (eg, genetics) may impact PK/PD in Japanese participants. Although Japanese participants may potentially have slightly higher exposure based on the lower mean body weight, the overall exposure in Japanese participants is predicted not to exceed established safety margins.

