## **Type of Participant**

- 2. Participants who are healthy as determined by medical evaluation including medical history, physical examination, laboratory tests, and cardiac monitoring.
- 3. Participant agrees to not donate blood for 4 months after completion of their last study visit.
- 4. Baseline IgG concentrations ≥ 1,000 mg/dL at Screening.
- 5. Baseline IgA and IgM above the lower limit of normal at Screening.
- 6. Participants must have had vaccination against pneumococcus (Pneumovax 23 [PPSV23]) at least 28 days, and maximally 4 years prior to Day 1.
- 7. Participants must have had seasonal influenza vaccination for the current season at least 28 days prior to Day 1.
- 8. Participants of Japanese descent (Cohort 6) are defined as:
  - a. First generation (born to 2 Japanese parents and 4 Japanese grandparents).
  - b. Participant must have been born in Japan, and not have lived outside Japan for greater than 10 years.
  - c. Lifestyle, including diet, must not have significantly changed since leaving Japan.

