# 7.2. Stopping Criteria

#### 7.2.1. Immunoglobulin Stopping Rules

It is proposed that the lower limit of IgG will be set at  $\leq 300$  mg/dL as an individual stopping rule for the healthy participant study. More specifically, if any predose measurements show a reduction of IgG level to  $\leq 300$  mg/dL, the individual stopping rule will be met. Repeat testing to confirm the consistency of the result is permitted. Healthy participants can rebound to their baseline IgG level when the drug is discontinued because they are not immunocompromised, as evidenced by existing anti-FcRn studies. Additionally, risk mitigation strategies such as antibiotics or IVIG replacement therapy may be implemented if participants have laboratory evidence of infection and/or are clinically symptomatic.

If 2 or more participants in a cohort exhibit IgG reduction to  $\leq 300 \text{ mg/dL}$ , dosing in that cohort/dose level will stop and no further dose escalation will occur.

In addition, any participant for whom IgA or IgM falls below the normal limits (according to the reference ranges of the laboratory) and is associated with clinical signs and symptoms will be discontinued from further dosing.

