#### **Cohort and Study Level:**

- A cohort and other cohort with a dose at an equal or higher level will be stopped or not initiated if any of the following occurs:
  - 2 participants on study drug in the cohort experience a moderate (Grade 2) AR
     that does not improve by 14 days after treatment
  - $\geq$  2 participants on study drug in the cohort experience an IRR as described earlier (see individual level)
- Study will be discontinued (all dosing [lower, equal, or higher doses]) and continuation of the cohort or study will require a substantial amendment, if any of the following occurs:
  - Two participants on study drug in any cohort experience a severe (Grade 3) AR
  - One participant on study drug in any cohort experiences a serious AR

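### For opening Cohort 6, Table 15 sets the minimum Cohort 5 data at Day 22, the day of the last dose, while Section 4.3 requires safety data through Day 36 and from all prior cohorts

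*Protocol*

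**What the plan says.** Section 4.1 of the protocol refers to Tables 14 and 15 for the timing and dependencies of the cohorts. The Cohort 6 row of Table 15 gives the Safety Review Committee (SRC) this minimum: "Review all available safety data and IgA, IgG, and IgM data through Day 22 from Cohort 5". It names no other cohort.

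Section 4.3 deals with the same decision in a paragraph that opens by citing Table 15. It says the exact Cohort 6 dose and time of dosing will be settled "after SRC review of all safety data through Day 36 from Cohort 5 as well as from all prior cohorts".

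Section 7.2.2 contains a rule that bears on the same gate: "A cohort and other cohort with a dose at an equal or higher level will be stopped or not initiated" if, among other triggers, 2 participants on study drug in the cohort have a Grade 2 adverse reaction (AR) "that does not improve by 14 days after treatment".

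Both gate statements are in the current text; neither comes from the amendment summary.

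**The concern.** One decision has two different data requirements, and the table, which is where a committee would look, has the weaker one. A review at Day 22 would satisfy Table 15 and fail Section 4.3.

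The decision settles whether Cohort 6 starts and at what dose. Cohort 6 is planned as 8 healthy participants, 6 on ALXN1830 and 2 on placebo, each given four weekly doses at the highest tolerated dose. An SRC working from the table alone would judge the tolerability of a four-dose regimen on the day of the fourth dose. It could not yet apply the 14-day Grade 2 rule to that dose, although the rule allows for not initiating a cohort as well as for stopping one.

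**Working it through.** The check is a comparison of texts plus calendar arithmetic. No power or error-rate figure is involved.

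**Dose days.** Tables 10 and 11 schedule weekly dosing in Cohorts 4 to 6. Day of dose k = 1 + 7(k − 1), which gives Days 1, 8, 15 and 22. Table 12 has no dosing, so Day 22 is the last dose.

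**The two requirements side by side.**

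| | Table 15, Cohort 6 row | Section 4.3 |
|---|---|---|
| Cohort 5 cut-off | Day 22 | Day 36 |
| Follow-up after dose 4 | Day of dosing only (22 − 22 = 0 days) | 36 − 22 = 14 days |
| Prior cohorts | Not named | All |
| IgA, IgG, IgM | Required | Not mentioned |

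**Safety data between the two cut-offs.** On Day 22 after dosing, Table 11 schedules vital signs, ECG, infusion site evaluation and immunoglobulin samples, the last at 12 hours. It schedules no hematology, biochemistry, coagulation or urinalysis that day. After dose 4:
- hematology first falls on Day 23;
- biochemistry, coagulation and urinalysis first fall on Day 25, with hematology repeated;
- ECGs run daily from Day 23 to Day 29;
- symptom-directed physical examinations fall on Days 25 and 29.

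A Day 22 cut therefore assures no safety laboratory result after the last dose. A Day 36 cut takes in all of the above, plus adverse events over 14 days.

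**The Grade 2 AR rule.** Window end = dose day + 14.

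| Dose | Day | Window ends | Complete by Day 22 | Complete by Day 36 |
|---|---|---|---|---|
| 1 | 1 | 15 | yes | yes |
| 2 | 8 | 22 | yes | yes |
| 3 | 15 | 29 | no | yes |
| 4 | 22 | 36 | no | yes |

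By Day 22, 2 of 4 windows are complete; by Day 36, all 4. If the 14 days are counted from the last dose only, the rule cannot be applied before Day 36. The Day 36 visit has a window of ±1 day, so it can fall 13 to 15 days after dose 4.

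**When the rule reaches Cohort 6.** Section 4.3 allows Cohort 6 to be dosed at up to 1500 mg or up to 2250 mg. At 2250 mg, its dose equals that of Cohort 5, and a trigger in Cohort 5 would bar it from starting. At 1500 mg the rule would not bar it on Cohort 5 results, but those results decide which dose counts as tolerated.

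**The case against.** The strongest reply is that the table does no harm. Its column heading begins "Minimum Data to be Looked at (in Accordance With the CSP", so the row sets a floor, and a committee that follows Section 4.3 meets both texts. This stands as far as it goes. A reader might infer that the protocol permits Cohort 6 to open once Cohort 5 reaches Day 22. The documents do not support that, because Section 4.3 separately fixes what must be reviewed. What remains is a floor set below another binding section.

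A second reply is that the Day 22 limit may apply only to the immunoglobulin data, leaving the available safety data uncapped. With the stagger of at least 7 days in Section 4.1, the first four participants would be at Day 29 or later when the last reach Day 22. Even so, the row would not require Day 36 data or prior-cohort data. The table footnote ties the dose to the highest tolerated dose in the non-Japanese cohorts, which implies that earlier results are used but does not state what must be reviewed.

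Third, Day 22 is also the cut-off in the Cohort 4 and Cohort 5 rows. A reader might infer that those rows are wrong too. No other text contradicts them, so they are outside this point. The 14-day rule supports Day 36 for Cohort 6, but the error rests on the conflict with Section 4.3.

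Fourth, a reader might infer that a Day 22 review would miss a breach of the IgG limit. Entry requires "Baseline IgG concentrations ≥ 1,000 mg/dL at Screening", and Section 4.3 says the "expected maximum IgG reduction after 4 qw doses is expected to be around 69% and 72%, respectively" for 1500 mg and 2250 mg. At 72%, 1,000 × (1 − 0.72) = 280 mg/dL, below the 300 mg/dL limit; any baseline up to 300 / 0.28 = about 1,071 mg/dL would reach it. The documents do not carry this further:
- The individual rule in Section 7.2.1 uses predose measurements, and the last of these is on Day 22, inside the table's cut.
- The two-participant rule there says "dosing in that cohort/dose level will stop and no further dose escalation will occur", but Section 4.2 words it for the cohort alone, without the dose level.
- Section 10.7.1.1 expects falls of no more than about 70% and IgG staying above 300 mg/dL.
- The day of the IgG low is not given.
- Section 4.3's Day 36 covers safety data only.

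Fifth, the row gives no number of participants, unlike the rows for Cohorts 2, 4 and 5. That is an ambiguity, since it can mean the whole cohort.

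Lastly, other safeguards exist. The stopping rules keep running, and Cohort 6 has its own 7-day stagger after its first 4 participants (3 active, 1 placebo). These act once Cohort 6 has begun, whereas Section 7.2.2 also provides for not starting it. The SRC charter, which also sets the data for each review, and the meeting dates in Figure 1 were not available to check. Neither would remove a contradiction within the protocol.

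**Conclusion.** The inconsistency is real and worth correcting. The Cohort 6 row of Table 15 falls short of Section 4.3 by 14 days of Cohort 5 safety follow-up and omits the prior cohorts. Day 36 is the coherent threshold: Section 4.3 names it, and it closes the 14-day AR window for dose 4, subject to the ±1 day visit window.

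The finding is confined to a wrong threshold in the operational table. It does not show that an early start was authorised, that an IgG stopping rule would have been missed, or that the other Day 22 rows are faulty. It assumes that Section 4.3 states the intended requirement and that the 14 days in Section 7.2.2 run from a dose.

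Realised impact is nil. The SAP (Section 4.1) records that the study was terminated early and that Cohort 6 has no participants, so no participant or analysis was affected.

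**What to change.** Change the minimum-data cell of the Cohort 6 row to: *All available safety data through Day 36 from Cohort 5 and from every prior cohort, plus IgA, IgG and IgM results from Cohort 5 through at least Day 22.* Align the SRC charter if it copies the row.

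Extending the immunoglobulin cut to Day 36 is optional. Samples are already scheduled on 8 days after Day 22 (Days 23 to 29 and Day 36), but Section 4.3 does not ask for them at this gate.

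The cost is one table row and, at most, about 14 days before Cohort 6 starts. There is no delay if the SRC already follows Section 4.3. No visit, sample or analysis is added.
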